Outcome measures at the *activity level* of the International Classification of Functioning, Disability and Health (ICF) Model will include the Gross Motor Function Measure (GMFM), Peabody Developmental Motor Scales-2 (PDMS-2), Functional Mobility Scale (FMS), the Timed 10-meter Walk Test, the 1-minute Walk Test and the StepWatch accelerometer. Outcome measures at the *participation level* of the ICF Model will be the Pediatric Evaluation of Disability Inventory Caregiver Mobility Scale (PEDI). Videotapes of assessments will be scored by an assessor blinded to group allocation for the GMFM and PDMS-2. StepWatch data will be collected for all awake daytime hours over a 7 day period at study onset before treadmill training commences and at each of the post-intervention assessments. The StepWatch monitor will be secured around the child's ankle with a small knit cuff. [name] has successfully employed this method of monitor attachment in toddlers with and without motor limitations.^{23,36} StepWatch outcomes will be average number of strides/day and the percentage of the time walking.

[figure not shown]
In order to address specific aim # 1 (optimal parameters for dosing home-based treadmill training by comparing high-intensity to low-intensity treadmill training) and specific aim # 2 (effects of high- versus low-intensity treadmill training on walking attainment and overall walking activity), between-group differences of all the outcome measures will be analyzed as described in the next section. Specifically, between-group differences in GMFM and PDMS-2 will examine the effects of dosage on walking attainment and skills related to standing and walking. The changes in support needed for walking will be measured by the FMS in the two groups. Differences in walking speed and walking endurance will be analyzed using the data from the Timed 10-meter Walk Test and the 1-minute Walk Test, respectively. The parent perspective on overall child mobility will be analyzed by using the PEDI. Finally, overall walking activity will be shown by between-group differences from the StepWatch data.

Data Analysis

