A one-way analysis of variance (ANOVA) with repeated measures will be used for comparison of treatment groups for parametric dependent variables, i.e. PDMS-2, GMFM, Timed 10-meter Walk Test, and 1-minute Walk Test. Analysis for non-parametric data for dependent variables, i.e. PEDI and FMS, will be conducted using the Friedman test for comparison between groups. StepWatch data will be examined with the Wilcoxon sign rank test for paired data. Post hoc tests will be performed where appropriate. Alpha will be set at 0.05. In addition, data on whether children reached the minimum clinically important change will be reported for the GMFM.³⁷

[figure not shown]
Study Timeline

Overall Study Timeline

Study recruitment will commence as soon as all study sites have signed the cooperative IRB agreement. All equipment will be ordered immediately after the receipt of the grant. Training on StepWatch use will be conducted by [name] at Seattle Children's Research Institute. [name] and [name] will participate. During the same meeting, reliability training will be conducted on other outcome measures. Recruitment and enrollment will commence immediately by distributing study information at the three sites. It is anticipated that there will be coinciding intervention and data collection for the 8 children at each site for the duration of 15 months. Two treadmills will be available at each site for the 6-week treadmill intervention periods for each child. Video review will be ongoing by the consultant, who is blinded to group allocation, as the videos become available for each child. Preliminary data analysis will be conducted in order to present initial results at conference within the grant period. Once all data is collected, there will be a second on-site meeting of the three PIs in order to assure consistent data entry and to allocate the responsibilities for study result dissemination. All three investigators will engage in manuscript preparation with [name] as first author. Data analysis will be performed by a statistician at the lead institution in collaboration with the PIs. Manuscript preparation will be conducted in the final two months of the 24-month study period.

Study Timeline for Each Subject

As indicated above, each child will be enrolled in the study for a total period of 26 weeks.

Human Subjects

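### The dosing aims rest on all outcomes at alpha 0.05 with no primary test; if dose has no effect, two outcomes alone carry about a 7-10% chance of a false dose claim

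*Combined protocol and SAP*

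**What the plan says.** The Methodology section states how both specific aims will be answered: "between-group differences of all the outcome measures will be analyzed as described in the next section". It then assigns measures to questions. For walking attainment, "between-group differences in GMFM and PDMS-2 will examine the effects of dosage on walking attainment". FMS covers support needed, the two walk tests cover speed and endurance, PEDI covers the parent's view, and StepWatch covers overall walking activity. StepWatch yields two endpoints: "StepWatch outcomes will be average number of strides/day and the percentage of the time walking". That makes seven instruments and eight endpoints, each assessed at baseline and at three later visits.

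The Data Analysis section assigns a repeated-measures ANOVA, described as one-way, to PDMS-2, GMFM and the two walk tests. For the rest, "PEDI and FMS, will be conducted using the Friedman test for comparison between groups", and "StepWatch data will be examined with the Wilcoxon sign rank test for paired data". It closes with "Post hoc tests will be performed where appropriate. Alpha will be set at 0.05".

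The Power Analysis sizes the trial twice: 9 per group for PDMS-2 Locomotion change at 95% power (effect size 1.87 in the Fig. 4 caption), and 12 per group for a StepWatch difference of 3000 strides per day at 80% power. The first calculation is tied to walking attainment and the second to overall walking activity. Neither measure is called primary. The Data Analysis section lists PDMS-2 without naming the Locomotion subscale.

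Under Study Timeline, "Preliminary data analysis will be conducted in order to present initial results at conference within the grant period".

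**The concern.** The aim is to learn which training intensity is better, and several outcomes may each answer it at 0.05. The available text does not say which outcome decides, or whether the decision rests on one visit or on a test over all visits. Nothing in it therefore stops a single p-value below 0.05, on any measure, from being presented as the dose effect. Under no dose effect, the chance of at least one such result is above the stated 0.05.

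Taking the questions one at a time does not remove the problem, because GMFM and PDMS-2 are both assigned to walking attainment without a ranking. Results will also be looked at before data collection ends, for a conference. A primary test named after that point could no longer be shown to have been chosen independently of the results.

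**Working it through.** **Inputs from the documents.** Alpha 0.05 (Data Analysis); 12 children per group (Enrollment procedures); effect size 1.87 and 9 per group for PDMS-2 Locomotion, 3000 strides per day with 12 per group and 80% power for StepWatch (Power Analysis).

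**Assumptions.** Two-sided tests (sidedness is not stated). One test per endpoint. A common correlation rho between outcomes, shown from 0 to 0.9 because the documents give none.

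**Step 1: the plan's own sample size.** For a two-sample t-test with d = 1.87 and two-sided alpha 0.05, noncentral-t power is 93.5% at 8 per group and 96.1% at 9. So 9 per group (18 in all) is the smallest size reaching 95%, and the plan's figure reproduces. At 12 per group the power is 99.2%. The StepWatch figure cannot be reproduced because no SD is given. With 12 per group, 80% power implies d = 1.197, or an SD of 3000 / 1.197 = about 2,507 strides per day.

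**Step 2: chance of at least one false dose claim.** For k independent tests it is 1 - 0.95^k:
- k = 2: 1 - 0.9025 = 0.0975
- k = 4: 1 - 0.8145 = 0.1855
- k = 8: 1 - 0.6634 = 0.3366

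For equally correlated tests, write each z-statistic as sqrt(rho) U + sqrt(1 - rho) E with U shared. Then integrate 1 - [P(|z| < 1.96 given U)]^k over U.

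| Tests | rho 0 | 0.5 | 0.8 | 0.9 |
|---|---|---|---|---|
| 2 | 9.8% | 9.1% | 7.8% | 7.0% |
| 4 | 18.5% | 15.6% | 11.4% | 9.4% |
| 8 | 33.7% | 25.0% | 15.7% | 11.9% |

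Simulated t-tests with 12 per group agree to within about one percentage point. At rho 0.95 the values for four and eight tests fall to 8.0% and 9.5%. Only perfect correlation brings them to 5%.

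**Step 3: which row applies.**
- Two tests: GMFM and PDMS-2, or the two measures used for sizing. This is the smallest count that the plan's own structure supports.
- Four tests: the ANOVA outcomes. This row needs the ANOVA to include a group or group-by-time term, because a one-way within-child model does not test dose. It also needs enough children able to do the walk tests, which are given only to children who can walk with a device, and the children are pre-ambulatory at entry.
- Eight tests: only if PEDI, FMS and StepWatch receive valid between-group tests. The Friedman and paired signed-rank tests named in the plan do not compare independent groups.

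**Step 4: what the remedies do to power** (12 per group, the two measures independent). Let P be PDMS-2 power and S StepWatch power, with S = 0.800 at 0.05 and 0.699 at 0.025.
- Gated StepWatch power = P(0.05) x S(0.05). At d = 1.2: 0.802 x 0.800 = 0.642.
- Holm StepWatch power = S(0.025) + [S(0.05) - S(0.025)] x P(0.025). At d = 1.2: 0.699 + 0.101 x 0.701 = 0.770.
- Holm PDMS-2 power follows by exchanging the roles. At d = 1.2: 0.701 + 0.101 x 0.699 = 0.772.

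| PDMS-2 effect | PDMS-2 alone at 0.05 | StepWatch, gated | StepWatch, Holm | PDMS-2, Holm |
|---|---|---|---|---|
| 1.87 | 99% | 79% | 80% | 99% |
| 1.2 | 80% | 64% | 77% | 77% |
| 1.0 | 65% | 52% | 75% | 61% |
| 0.8 | 47% | 37% | 73% | 43% |

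**The case against.** The strongest reply is that the Power Analysis already implies one lead measure per question: PDMS-2 Locomotion for walking attainment and StepWatch for walking activity, matching the two parts of aim 2. The remaining outcomes describe separate constructs, and whether separate questions in a 24-child trial need joint error control is partly a matter of preference. This reduces the concern without removing it. Two lead measures tested without adjustment still give up to 9.8%, neither is ranked, and GMFM is also assigned to walking attainment.

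A second reply is that a repeated-measures test covers all visits at once, so no decisive visit is needed. That is correct if the group-by-time test is declared as the deciding one. The text does not do so and leaves post hoc tests open.

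A third is that a primary outcome might be named in a figure or an aims section that is not in the available text. This is possible but not shown, which is why the finding is limited to that text.

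A reader might also infer that the plan carries an error rate of 12-34%. The documents do not support that: the range applies only to a repaired plan in which all eight endpoints get valid between-group tests. Nor is eight an upper limit, since FMS is rated over three distances. The upper end of each range needs uncorrelated outcomes, which is unlikely for motor measures taken on the same children. Finally, the planned conference analysis does not show that anyone intends to select outcomes from it; the plan simply has no rule that prevents this.

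**Conclusion.** The concern holds in a limited form. The available text tests all outcomes for dose at 0.05 with no primary outcome, no deciding visit or overall test, and no multiplicity rule. With no dose effect and equal correlations of 0.9 down to 0, the chance of at least one false dose claim is about 7-10% on two outcomes. It is about 9-19% on the four ANOVA outcomes under the conditions in step 3. All of these exceed 5% unless the outcomes are perfectly correlated. The trial remains interpretable, but its dosing conclusion lacks a pre-specified basis. The change should be made because it is nearly free.

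**What to change.** Before any data are seen, including the preliminary conference analysis, state in the Data Analysis section:

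1. One primary test at two-sided 0.05, on which the dosing conclusion rests. The natural choice is PDMS-2 Locomotion, high versus low. It has the 95% power calculation and is scored blind from video: "Videotapes of assessments will be scored by an assessor blinded to group allocation for the GMFM and PDMS-2". Use either one group-by-time test over all visits, which needs no visit choice, or change from baseline to one pre-specified visit, which the sponsor selects.
2. StepWatch strides per day, compared between groups, as either (a) a key secondary tested at 0.05 only if the primary is significant, or (b) a co-primary with PDMS-2 under Holm, with a claim made per outcome.
3. All other outcomes and visits as supportive estimates with 95% confidence intervals, and post hoc tests only after a significant overall test.

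The cost is a paragraph of wording and no extra children, but it is not free of consequence. A lone significant secondary can no longer carry the conclusion. Under (a), StepWatch power stays near 79% only if the PDMS-2 effect really is 1.87, which the documents do not identify as a high-versus-low contrast; it falls to 64%, 52% or 37% at 1.2, 1.0 or 0.8. Under (b), it stays at about 73-80%, while PDMS-2 power drops slightly, for example from 80% to 77% at 1.2. If the sponsor doubts that the dose contrast will reach 1.87, (b) protects StepWatch better.

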- a diagnosis of a genetic disorder
- cardiac or orthopedic contraindications for standing and walking
- orthopedic surgery in the past 6 months
- use of spasticity-reducing medication or Botox injections in the past 6 months
- participation in other previous or concurrent intensive physical therapy programs

Interventions

All children will continue their regularly scheduled physical therapy during the study period. Frequency of ongoing physical therapy interventions as well as the physical therapy approach will be recorded for each child. All interventions will be conducted at the children's homes. On the first visit, the

PI will provide a portable pediatric treadmill for the family's use at no charge for the duration of the intervention period. The treadmill is designed for research and is equipped with a non-resettable minute timer and adjustable handle bars.²⁷ There will be a one-week training period for each child to familiarize the family with the treadmill intervention. After initial set-up of the treadmill, the PIs will conduct weekly visits to the family. The children will undergo 6 weeks of treadmill training in their homes administered by a parent or primary caregiver who has been trained to safely provide the intervention. The weekly visits will be conducted by the PIs to adjust the treadmill speed and make any needed corrections to the parents'/caregiver's technique.

Children assigned to the high-intensity group will walk on the treadmill 5 days/week, twice daily for 10-20 min for 6 weeks. Children in the low-intensity group will walk on the treadmill 2 days/week, once daily for 10-20 minutes for 6 weeks. The parents will be encouraged to take a break on two days of their choice, depending on the family's other commitments. The treadmill speed will be determined based on previous protocols developed by [name].¹⁷ The initial treadmill speed will be set at the maximum speed at which the child can maintain walking without dragging his/her feet for more than 3 seconds. The treadmill speed will be increased during the weekly investigator visits as tolerated by the child, using the same criterion. The children will wear shoes and/or their customary orthotics during the walking. The treadmill speeds will not exceed 0.6 meters/second, which is the maximal speed available on the pediatric treadmills. It is anticipated that all children will walk at a speed between 0.1 and 0.3 meters/second.

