Due to their young age, some of the children, particularly those in the high-intensity group, might have difficulty maintaining attention to the task during the intensive intervention. In order to keep them motivated during the treadmill walk, the treadmill will be placed in front of a TV or laptop showing an age-appropriate movie chosen by their parents. This technique has proven to be helpful in previous studies and has the added benefit of preventing the children from looking downward.^{17,20} In one previous study, the average daily time walked on the treadmill was 28.2 ± 11.2 minutes for the twice daily walking periods by a similar group of children using the above described motivational techniques.¹⁷

Some children might be unable or unwilling to hold onto the handle bars of the treadmill. In this case, a second parent will be necessary to help the child maintain grip of the handle bars. If a second person is not available, the child's hand can be loosely strapped onto the handle bar for the duration of the walk.

Outcome Measures

Each child will be tested at pre-intervention, post-intervention, at 1-month and at 4-months following the intervention.

Valid and reliable outcome measures at the *Body Structures and Functions Level* of the International Classification of Functioning, Disability and Health (ICF) Model²⁸ will include the 1-minute Walk Test. Outcome measures at the *Activity Level* of the ICF model will include the Gross Motor Function Measure-66 (GMFM-66), Peabody Developmental Motor Scales-2 (PDMS-2), Functional Mobility Scale (FMS), the Timed 10-meter Walk Test and the StepWatch accelerometer. Outcome measures at the *Participation level* of the ICF Model will be the Pediatric Evaluation of Disability Inventory Mobility Scale (PEDI). Videotapes of assessments will be scored by an assessor blinded to group allocation for the GMFM and PDMS-2.

- 1-minute Walk Test: The child's walking distance will be measured in meters over 1 minute at their self-selected walking speed if the child is able to walk with an assistive device. The 1-minute Walk Test is a reliable test of walking endurance in young children with CP, when administered after a practice trial. Due to the young age and early ambulatory status of the children, the 1-minute Walk Test is more appropriate than a 6- minute Walk Test.²⁹

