Each child will be tested at pre-intervention, post-intervention, at 1-month and at 4-months following the intervention. The testing will be scheduled at a mutually agreed-upon and convenient time with the family at their home. The children will undergo 6 weeks of treadmill training in their homes administered by a parent or primary caregiver who has been trained to safely provide the intervention. Weekly visits will be conducted by the researchers to adjust the treadmill speed and make any needed corrections to the parents' technique. The treadmill speed will be increased each week as tolerated by the child. The speed will not exceed 0.6 meter/second. In a previous study by [name] using a similar sample and treadmill protocol, the average starting speed was 0.1 meters/second and increased to an average of 0.25 meter/second over the duration of 6 weeks.¹⁷ Children assigned to the high-intensity group will walk on the treadmill 5 days/week, twice daily for 10-20 min for 6 weeks. Children in the low-intensity group will walk on the treadmill 2 days/week, once daily for 10-20 minutes for 6 weeks. The children will be motivated during the treadmill walk with a child-friendly video shown on a television, computer, or tablet. If uninterested, children will be encouraged with other motivational toys suggested by the parents. These motivational methods led to high adherence in [name] previous study on a similar sample of young children with CP.¹⁷

There is a possibility that a child might miss a training session due to sickness or other family obligations. The parents will be encouraged to make up a missed session on a different day. In the low-intensity group, the children have 5 days/week without treadmill training that could be used as make-up days. In the high-intensity group, the children have 2 days/week without treadmill training that could be used as make-up days. If a missed day cannot be made up, the parents will be encouraged to attempt to

train for the maximal 20 minutes for each treadmill walk in order to make up some of the missed minutes during other walks. The parents will document the minutes walked and the speed of each treadmill walk on a paper flow chart that is provided to them by the PIs.

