The study protocol was submitted to the Institutional Review Board (IRB) at California State University, Sacramento, on July 10, 2014 and approved on July 29, 2014 (IRB protocol #13-14-156). In addition, the consent form, permission to be videotaped, parent questionnaire and physician form for the study were all approved by the IRB. Once the grant is received, a cooperative agreement form will be signed by the two participating universities before the study commences.

Selection of the families will be made by judgment of the PI. Factors will include parental ability to correctly perform the treadmill training and safety during treadmill training sessions. The PIs reserve the right to terminate participation in the study if parents are unable to adhere to the agreed-upon treatment regimen, or display incorrect or unsafe technique during training. Any adverse events will be reported to the IRB. Because this intervention is conventionally used in physical therapy practice, adverse events are not anticipated. A small incentive will be offered to families to encourage participation. The families have the right to terminate participation in the study without any reason or penalty.

The study will be conducted in the children's homes. The last names of the children will not be used when other persons are present in the area. The PIs will abide by Health Insurance Portability and Accountability Act (HIPAA) regulations on children's privacy. When reporting results, only ages, diagnosis, functional level and gender of children will be reported. Photographs and/or video clips of children might be used when reporting results, but only with written permission of the parents/guardians. No mention of exact geographical location will be made.

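### The plan specifies no systematic, arm-neutral way to find harms, so any description of harms by training dose would be unreliable

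*Combined protocol and SAP*

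**What the plan says.** Human Subjects deals with adverse events in two sentences: "Any adverse events will be reported to the IRB. Because this intervention is conventionally used in physical therapy practice, adverse events are not anticipated". No definition, form, scheduled question or collection window appears there or elsewhere.

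On the training record, Methodology says: "The parents will document the minutes walked and the speed of each treadmill walk on a paper flow chart". On contact with families, Interventions says: "After initial set-up of the treadmill, the PIs will conduct weekly visits to the family". It gives the purpose: "The weekly visits will be conducted by the PIs to adjust the treadmill speed", together with correcting the caregiver's technique. Methodology repeats this purpose. Neither section mentions asking about events.

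The two schedules in Interventions are "Children assigned to the high-intensity group will walk on the treadmill 5 days/week, twice daily for 10-20 min for 6 weeks" and "Children in the low-intensity group will walk on the treadmill 2 days/week, once daily for 10-20 minutes for 6 weeks". A trained parent or caregiver gives the sessions at home. Interventions also expects that "some of the children, particularly those in the high-intensity group, might have difficulty maintaining attention to the task during the intensive intervention".

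Methodology states aim 1 as "optimal parameters for dosing home-based treadmill training by comparing high-intensity to low-intensity treadmill training" and ties it to between-group differences in the outcome measures. Harms are not among those measures, and Data Analysis contains no safety summary.

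**The concern.** A duty to report to the IRB says what happens to an event once it is known. It does not say how the event becomes known. The reassurance in Human Subjects rests on ordinary physical therapy practice, whereas here caregivers train pre-ambulatory children under three at home. The protocol itself foresees that a parent's technique may be unsafe (Methodology, Human Subjects) and that a child's hand may be loosely strapped to the bar when no second adult is available (Interventions).

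A conclusion about the best dose needs some account of harm and tolerability at each dose. The arms differ in exposure and in the share of sessions an investigator could see, so incomplete capture would not be neutral: proportionally more events would be lost in the high-intensity arm, which would make that dose look safer than it is. Events not recorded at the time cannot be reliably reconstructed later.

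**Working it through.** The plan gives no figure for harms or for the share of sessions observed, so there is none to reproduce.

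**Inputs**
- High intensity: 5 days × 2 walks a week for 6 weeks (Interventions).
- Low intensity: 2 days × 1 walk a week for 6 weeks (Interventions).
- Visits: weekly in both arms, taken as 6 over the training period (Interventions, Methodology).
- Children: 12 per arm (Enrollment procedures).
- Assumption: one session seen per visit. The documents do not say. The alternative is that both daily walks are seen in the high-intensity arm.

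**Exposure**
- High: 5 × 2 × 6 = 60 sessions per child; 12 × 60 = 720 per arm.
- Low: 2 × 1 × 6 = 12 sessions per child; 12 × 12 = 144 per arm.
- Ratio: 60 / 12 = 5. At 10 to 20 minutes a walk this is 600–1200 against 120–240 minutes per child.

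**Share directly observed**
- High: 6 / 60 = 10%, or 12 / 60 = 20% if both daily walks are seen.
- Low: 6 / 12 = 50%.
- Unobserved at one session per visit: 60 − 6 = 54 against 12 − 6 = 6 per child; × 12 = 648 against 72 per arm.

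**Expected events, with an assumed common risk per session**
- At 1%: 720 × 0.01 = 7.2 against 144 × 0.01 = 1.44. In observed sessions: 72 × 0.01 = 0.72 in each arm.
- Over 0.5% to 5%: from 3.6 against 0.72 up to 36 against 7.2. In observed sessions: 0.36 to 3.6 in each arm.

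**Allowing for parents' reports.** Let r be the share of events in unobserved sessions that parents volunteer, equal in both arms, and let every event in an observed session be captured. The captured share is 0.1 + 0.9r (high) and 0.5 + 0.5r (low). The ratio of known counts is (72 + 648r) / (72 + 72r), whatever the common risk.

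| r (assumed) | Captured, high | Captured, low | Known counts, high:low (true 5:1) |
|---|---|---|---|
| 0 | 10% | 50% | 1.0 |
| 0.25 | 32.5% | 62.5% | 2.6 |
| 0.5 | 55% | 75% | 3.7 |
| 1 | 100% | 100% | 5.0 |

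If both daily walks are seen, the high-intensity share is 0.2 + 0.8r and the ratio is (144 + 576r) / (72 + 72r): 2.0, 3.2, 4.0 and 5.0 for the same values of r. The distortion is smaller and in the same direction.

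**What complete collection could show at 12 against 12**
- No events in 12 children: one-sided 95% upper bound 1 − 0.05^(1/12) = 22%.
- Smallest split against zero with Fisher p < 0.05: 5/12 against 0/12, p = 0.037.
- Exact Fisher power at assumed rates: 9.5% for 10% against 30%, and 42.5% for 10% against 50%.

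**The case against.** Much can be said for the plan, and several stronger statements that a reader might infer do not stand.

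- *That IRB reporting is the only safety rule.* It is not. The plan excludes children with cardiac or orthopedic contraindications, caps speed, requires physician clearance, and provides for retraining or ending participation when technique is unsafe. These limit risk, but they do not collect harms.
- *That at most 10% of high-intensity sessions can be seen.* This assumes one session per visit; 20% is possible.
- *That unseen events are lost.* A caregiver is present at every session and meets an investigator weekly, and the IRB provision is not limited to witnessed events. Being observed is not the same as being ascertained. What stands is that nothing prompts the caregiver, and Human Subjects lets investigators end participation for unsafe technique, which could discourage volunteering.
- *That equal visit frequency is the defect.* Equal visits give both arms the same opportunity to report. The gap is the missing enquiry.
- *That tolerability cannot be compared.* Logged minutes and speed, a timer that cannot be reset, speed increases that depend on tolerance, and drop-outs all give partial data. But a walk cut short at 12 minutes falls within the prescribed 10 to 20, make-up sessions can mask poor tolerance in totals, and no analysis is planned.
- *That the protocol predicts more harm at high intensity.* It predicts difficulty with attention. The skin irritation mentioned in Human Subjects concerns the StepWatch strap, which both arms wear on the same assessment schedule.

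The chart itself is not reproduced, so only its stated fields are known. Handwritten notes and video of treadmill walking are mentioned, without a frequency or any review for harms. Finally, no harms comparison is planned, so a misleading finding of no difference is a risk of later interpretation, not a planned result.

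**Conclusion.** The concern holds in limited form. The plan specifies no definition, enquiry, form or by-arm summary for harms in a trial whose first aim is dosing. Planned exposure differs 5:1, and direct observation would cover about 10% (up to 20%) of high-intensity sessions against 50% of low-intensity sessions. Knowledge of other events depends on unsolicited reports, so a description of harms by dose would be unreliable and, at an equal reporting rate below 100%, would understate the difference between arms. Tolerability has partial data but no stated field for the reason a walk stopped and no planned analysis.

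The session counts follow from the schedules. The observed shares rest on six visits and on one or two sessions seen per visit. The per-session risks and reporting rates are illustrations with no source in the documents. The documents do not support saying that the trial is unable to compare harm or tolerability at all, or that harms are in fact higher in one arm.

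**What to change.** - **Chart:** add tick boxes for each session to the existing parent chart: fall or slip; injury, pain or skin mark; distress; stopped early, and why. Include the one-week training period.
- **Enquiry:** ask one fixed adverse-event question, worded identically in both arms and at all three sites, at each existing weekly visit and each assessment.
- **Analysis:** in Data Analysis, plan a descriptive table by arm of children with an event, events per child, events per session, and minutes completed against schedule. Include every child who used the treadmill, also those reported as drop-outs. Methodology now leaves out the data of a child stopped because a parent cannot train safely, and that child matters for safety.
- **Interpretation:** state that 12 per arm allows description and not a powered comparison of harms, and that any conclusion on the optimal dose will be read alongside these counts.

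The cost is a few fields on an existing form, one question at existing contacts and one table, with no new visits or staff. The downside is slightly more recording by parents and more minor events on file, probably mostly in the high-intensity arm because it has more sessions. Events per session should therefore stand beside the counts per child.
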